### 5.1.6 Rescue Procedures

If PaO2 ≥ 55 mmHg or SpO2 ≥ 88% with FIO2 of 1.0 cannot be maintained or if acidosis is severe and cannot be controlled, and alternate therapies (rescue procedures) can be employed. Rescue procedures will be chosen according to the University of Michigan ARDS protocol (Appendix C), and may include repeated recruitment maneuvers, prone positioning, neuromuscular blockade, inhaled nitric oxide, inhaled epoprostenol sodium, airway pressure release ventilation, high frequency ventilation, or ECMO.

### 5.1.7 Other Aspects of Care

All other aspects of care such as fluids, antibiotics etc. will be determined by the clinical team caring for the patient.

## 6 Data Collection

### 6.1 Background Assessments

1. Demographic and Admission Data (including age, sex, race)
2. Pertinent Medical History and Physical Examination (including Charlson co-morbidity score)
3. Height; gender; measured Body Weight (mBW); calculated predicted body weight (PBW); body mass index (BMI)
4. Time on ventilator prior to enrollment
5. Risk factors for ARDS (sepsis, aspiration, trauma, pneumonia, drug overdose, other)
6. Ever smoker (>100 cigarettes in lifetime)?
  - a. If Yes, current smoker?
  - b. If ever smoker, estimate pack years [Pack years = (# packs per day) x (number of years smoked)]
  - c. If former smoker, when quit?

## 6.2 Baseline Assessments

The following information will be recorded during the 24-hour interval preceding randomization. If more than one value is available for this 24-hour period, the value closest to the time of randomization will be recorded. If no values are available from the 24 hours prior to randomization, then values will be measured post randomization but prior to study initiation.

1. History and physical examination
2. Vital signs: heart rate (beats / min), systemic systolic and diastolic BP (mmHg), body temperature (°C)
3. Ventilator mode, rate, minute ventilation, tidal volume, FiO2, PEEP, Pplat, Ppeak, and Pmean
4. Arterial blood gas (PaO2, PaCO2, SaO2, pH) and SpO2
5. Frontal Chest Radiograph – radiographic lung injury score (# of quadrants)
6. Administration of the following medications (name)
  - (a) Sedatives
  - (b) Analgesics
  - (c) Vasopressors
  - (d) Corticosteroids
7. Presumed site of infection, if sepsis is the etiology of ARDS
8. APACHE II score, including the acute physiology components
9. APACHE II demographics plus history of: hypertension, prior myocardial infarction, congestive heart failure, peripheral vascular disease, prior stroke with sequelae, dementia, chronic pulmonary disease, arthritis, peptic ulcer disease
10. SOFA Score: Cardiovascular, renal, respiratory, hepatic, and hematology organ function will be assessed using the SOFA methodology as described in Appendix H.

## 6.3 Assessments During Study

The following data will provide the basis for assessing protocol compliance and safety as well as between-group differences in several efficacy variables. Data for each of the variables will be recorded at the times shown in the Time-Events schedule (Appendix F).

It is expected that setting PEEP using EIT will take between 20-40 minutes and 5-10 minutes using the High-PEEP table. To standardize the time from new PEEP exposure until inflammatory mediators are obtained, time 0 is defined as the time at which the PEEP setting is finally established. Hour 6 is subsequently six hours after PEEP is initially established and the time of the 2nd mini-BAL. Time 0 resets at the point of crossover, as the time at which the new PEEP level is established. (see Appendix F)

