## 3 End Points

- The protocol duration is 24 hours.

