#### PEEP Titration Procedure:

1. The procedure involves two phases: a recruitment phase followed by a gradual reduction in the end-expiratory pressure phase (Decremental PEEP).

2. Recruitment Phase: Pressure control with a drive pressure of 15 cm H2O and PEEP of 20 cm H2O (ie, 35/20) will be applied for 5-10 breaths and then increased to a PEEP of 25 cm H2O (ie, 40/25) for 1 minute.
3. Decremental PEEP: In volume control, VT will be set to 6 mL/kg PBW and PEEP to 20. Every 5-10 minutes, PEEP will be reduced by 2 cm H2O. PEEP will be reduced until one of the following occurs: 1) drop in EELI in any region during the stabilization period by >10%, 2) PEEP = 5 cm H2O, or 3) patient develops hemodynamic instability or SpO2 <88%.
4. The best EIT-PEEP is identified as that which demonstrates the best compromise in over-distension (OD) and collapse (CL), as determined by the ODCL EIT variable.

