## F. Time-Event Schedule

Clock example	Study hour	Procedures	Vent data	EIT data	HR/ BP	SpO2	ABG	Cytokines	Comments
closest	BL, pre	BL Assess	X		X	X	X		
8:00		BAL#1			X	X		X	BAL procedure time ~30 min
8:30	0	Set PEEP #1	X	X	X	X			Set EIT ~20-40 min vs table ~5-10 min
9:30	1						X	X	ABG 1 H after setting PEEP
10:30	2								
11:30	3								
12:30	4								
13:30	5								
	pre BAL	Assessment	X	X	X	X	X		
14:30	6	BAL #2			X	X		X	BAL procedure time ~30 min
15:00	0	Set PEEP #2	X	X	X	X			
16:00	1					X	X		ABG 1 H after setting PEEP
17:00	2								
18:00	3								
19:00	4								
20:00	5								
21:00	6								
22:00	7								
23:00	8								
0:00	9								
1:00	10								
2:00	11								
3:00	12								
4:00	13								
5:00	14								BAL #3, anytime between hr 14-18
6:00	15								
7:00	16								
8:00	17								
9:00	pre-BAL	Assessment	X	X	X	X	X		
9:00	18	BAL #3			X	X		X	BAL procedure time ~30 min

Data Collected:	Ventilator: mode, set VT, RRset, RRtot, VE, FiO2, PEEP, Ppeak, Pplat, Pmean, PEEPtot,
	vent calcs: drive-P, Cst, Cdyn,
	EIT: delta-EELI, ODCL; COV, GI Index, Regional compliance
	ABG: pH, PaCO2, PaO2, SaO2, BE, HCO3 (if collected for standard of care)
	Cytokines: per protocol

**Definition of Time:** Time 0 is when PEEP is established

Time 6 is 6 hours after PEEP is set

Reset time frames at cross-over

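### The 24-hour protocol and adverse-event period do not fit the plan's own schedule when the third mini-BAL is taken late in its 14-18 hour window

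*Combined protocol and SAP*

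**What the plan says.** **Duration and safety period.** Section 3: "The protocol duration is 24 hours". Section 11 has adverse events assessed from enrollment to the end of the protocol, which it places 24 hours after enrollment. Sections 5.1.3 and 5.1.4 instead end the protocol once the third mini-BAL is done.

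**Sequence.** Each patient has a mini-BAL, a first PEEP setting, a second mini-BAL at hour 6, a second PEEP setting by the other method, and a third mini-BAL 14-18 hours later. Section 6.3 starts the clock (time 0) only when the PEEP level has been settled, and restarts it at crossover. Appendix F gives each mini-BAL about 30 min.

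**Time to set PEEP.** Section 6.3: "It is expected that setting PEEP using EIT will take between 20-40 minutes", against 5-10 min for the table. Appendix F repeats this: "Set EIT ~20-40 min vs table ~5-10 min".

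**EIT steps (Section 5.1.5).** After a short recruitment phase, "VT will be set to 6 mL/kg PBW and PEEP to 20"; then "Every 5-10 minutes, PEEP will be reduced by 2 cm H 2 O". The run ends at the first of three events: "1) drop in EELI in any region during the stabilization period by >10"% (the EELI criterion), PEEP of 5, or "patient develops hemodynamic instability or SpO 2 <88"% (the safety criterion).

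**The concern.** The 24-hour figure does two jobs: it describes the study, and it closes the adverse-event period. The third mini-BAL is an invasive study procedure in hypoxemic patients. Section 9.1 lists pneumothorax, bleeding and hypoxemia among its risks, requires observation for 15 minutes afterwards, and makes early termination a reportable adverse event. If the schedule lets this procedure start or finish after hour 24, the period for collecting its complications has closed under one reading of Section 11.

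The example clock and the expected titration time feed the same schedule. If they leave out time that the steps require, staff planning from Appendix F will find the last procedure later than printed.

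**Working it through.** **The plan's own figures.** The documents do not derive the 24 h. The upper exposure times alone give 6 + 18 = 24 h, leaving nothing for mini-BALs or setting PEEP. The 20-40 min figure is reproduced by four levels (20, 18, 16, 14): 4 x 5 = 20 min and 4 x 10 = 40 min.

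**Full EIT run.** Holding 20, 18, 16, 14, 12, 10, 8 and 6 is eight levels: 8 x 5 = 40 min to 8 x 10 = 80 min. Steps of 2 from 20 never land on 5, so the last step is open to interpretation; seven or nine levels give 35-70 or 45-90 min. Eight levels fit within 40 min only if every dwell is the 5-min minimum.

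**Total time**, start of first mini-BAL to end of third, in minutes:

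30 + first setting + 360 + 30 + second setting + (840 or 1080) + 30

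Every patient has one EIT and one table setting, so the total is the same in either order. Without setting time it is 450 + 840 = 1290 min, or 450 + 1080 = 1530 min.

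| Setting time assumed | Both settings together | Third mini-BAL at hour 14 | At hour 18 | Latest hour that ends by 24 h |
|---|---|---|---|---|
| None (clock as printed) | 0 min | 21.5 h | 25.5 h | 16.5 |
| As stated (EIT 20-40, table 5-10) | 25-50 min | 21.9-22.3 h | 25.9-26.3 h | 15.7-16.1 |
| Full EIT run (40-80, table 5-10) | 45-90 min | 22.3-23.0 h | 26.3-27.0 h | 15.0-15.8 |

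The last column is 24 h minus 7.5 h (450 min) minus setting time. The 15-minute observation adds 0.25 h to every total.

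**Check against the printed clock.** Appendix F starts the first mini-BAL at 8:00 and puts the hour-18 mini-BAL at 9:00 next day. That is 25.0 h later, ending at 25.5 h, as in the first row.

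**Check with the other anchor.** Sections 5.1.3 and 5.1.4 place the second mini-BAL about six hours after randomization. Then, with no second setting time, the third ends at 6 + 0.5 + 14 + 0.5 = 21.0 h or 6 + 0.5 + 18 + 0.5 = 25.0 h after randomization. Hour 18 still exceeds 24 h.

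**Appendix F against time 0.** The first mini-BAL starts at 8:00 and takes about 30 min, and hour 0 is 8:30. The second starts at 14:30, and hour 0 is 15:00. Time 0 comes after PEEP is set, so both settings are given 0 min, although the same table prints 20-40 and 5-10 min for them.

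**The case against.** **The 20-40 min figure is an expectation, not a ceiling.** The run stops at the first of three events, and only one needs a full descent. A reader might infer that 20-40 min contradicts the steps. The documents do not support that: a stop after four levels gives exactly this range. What stands is that the assumed stop is not stated. Appendix E offers some reason to expect longer runs (a mean EIT PEEP of 11.3 in the 39-patient ARDS series, and a mean of 48 min to complete the 16-patient study), but methods differ and this is only indicative.

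**Belt time may not be extra.** Section 5.1.5 allows 5-10 min for electrode stabilization, but EIT data are recorded at hours 0 and 6 whichever method comes first, so the belt may already be on. The text does not say whether the 20-40 min includes it.

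**Titration time does not cause the 24-hour conflict.** A reader might infer that slow titration pushes the third mini-BAL past 24 h. But hour 18 fails with no setting time, and hour 14 passes with an 80-min run. The cause is the 14-18 hour window set against 24 h; longer titration only adds to it.

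**Planned exposure is protected.** Under Section 6.3 the 6-hour and 14-18-hour exposures run from time 0, so a longer titration moves clock times and leaves exposure unchanged. The randomization anchor in Sections 5.1.3 and 5.1.4 is a separate inconsistency.

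**Collection may continue in practice.** Section 11 also refers to the end of the protocol, which Sections 5.1.3 and 5.1.4 tie to the third mini-BAL, and Section 9.1 requires early termination to be reported without a time limit. So the documents do not show that late events will be lost. They give two end points that can differ, and one closes first.

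**Conclusion.** The 24-hour duration and adverse-event period are inconsistent with the plan's own schedule. At hour 18 the third mini-BAL ends 1.5 h late with no setting time, 1.9-2.3 h late with the stated times, and 2.3-3.0 h late after a full EIT run. At hour 14 it ends within 24 h in every case tabulated.

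These figures assume 30 min per mini-BAL, no other delays, and enrollment at the start of the first mini-BAL, which favours the plan because consent and randomization come first. The hour-14 margin is 2.5 h with no setting time and 1.0 h after the slowest eight-level run; an earlier enrollment time uses it up.

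Two smaller points stand on their own: the assumption behind 20-40 min is unstated, and the Appendix F clock omits setting time. No effect on a biomarker or physiologic comparison is shown.

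**What to change.** Reconcile Sections 3, 5.1.3, 5.1.4, 5.1.5, 6.3 and 11 with Appendix F:

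- Restate the total duration so that it agrees with the sampling window.
- Define the adverse-event period to run through the post-procedure observation after the third mini-BAL.
- Show the time for setting PEEP before each hour 0 in the example clock.
- State the stop level assumed for 20-40 min or give the full-run range of 40-80 min, and say whether belt set-up is included.

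The cost is wording, a corrected example clock and slightly longer safety collection for some patients: up to 27.0 + 0.25 - 24 = 3.25 h on the assumptions above. No change to the titration rule or to any other clinical rule is proposed.

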### Safety assessment during the mini-BAL

1. Heart rate, blood pressure and SpO2 will be continuously monitored

### Hour 0 of First group (following initial PEEP setting):

1. Ventilator mode, rate, minute ventilation, tidal volume, FiO2, PEEP, Pplat, Ppeak, Pmean, total-PEEP
2. EIT data
3. Heart rate, systemic systolic and diastolic BP, SpO2

### Hour 1 of First group:

1. Arterial blood gas (pH, PaCO2, PaO2, SaO2), if collected for standard of care
2. SpO2

### Hour 6 of First group:

1. Immediately before the mini-BAL
  - a. Ventilator mode, rate, minute ventilation, tidal volume, FiO2, PEEP, Pplat, Ppeak, Pmean, total-PEEP
  - b. EIT data
  - c. Heart rate, systemic systolic and diastolic BP, SpO2
2. Safety assessment during the mini-BAL
  - a. Heart rate, blood pressure and SpO2 will be continuously monitored
3. Immediately following the mini-BAL, the patient will crossover to the other PEEP titration method

### Hour 0 of Crossover group (following initial PEEP setting):

1. Ventilator mode, rate, minute ventilation, tidal volume, FiO2, PEEP, Pplat, Ppeak, and Pmean, total-PEEP
2. EIT data
3. Heart rate, systemic systolic and diastolic BP, SpO2

### Hour 1 of Crossover group:

1. Arterial blood gas (pH, PaCO2, PaO2, SaO2), if collected for standard of care
2. SpO2

### Hour 14 to 18 of Crossover group:

1. Immediately before the mini-BAL
  - a. Ventilator mode, rate, minute ventilation, tidal volume, FiO2, PEEP, Pplat, Ppeak, and Pmean, total-PEEP
  - b. EIT data
  - c. Heart rate, systemic systolic and diastolic BP, SpO2
2. Safety assessment during the mini-BAL
  - a. Heart rate, blood pressure and SpO2 will be continuously monitored
3. Immediately following the mini-BAL, the patient will be placed on standard University study ventilator settings and the study will conclude

## 7 Statistical Considerations

This study will compare the physiologic and biomarker endpoints from various time points: Usual care first and EIT first groups will be compared with each other at baseline and between groups at 6 hours. The 6-hour crossover point will yield a comparison between groups 14-18 hours later, at the completion of the protocol as well as a comparison between groups from the 6-hour crossover point. Quantitative, normally distributed variables such as cytokine levels and P/F ratio will be tested via t-test. Quantitative, non-normally distributed variables such as driving pressure and plateau will be tested via Mann Whitney test. Categorical variables, such as cause of ARDS will be tested via Chi-square.

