## 1.1 STUDY RATIONALE

To date, studies of EIT in ARDS patients have only assessed the distribution of ventilation and not whether lung inflammation is decreased. Our research goals are to assess markers of lung inflammation: IL-6, IL-8, TNFR1, sRAGE, SP-D, Angiopoentin-2, and VWF in conjunction with ventilator changes made in ARDS patients correlated with EIT in order to determine whether the optimization of mechanical ventilation may be achieved by this means.

One arm of the protocol will have best PEEP determined by oxygenation response using a PEEP/FiO2 combination table, similar to the one used in the LOVS protocol [11]. A modified version of the LOVS's table (High-PEEP) has been incorporated into the University of Michigan ARDS protocol. EIT findings will be determined but the bedside respiratory therapist will be blinded to the EIT findings during this arm of the protocol. Alternatively, in the second arm of the protocol, EIT will be used to determine the best PEEP – i.e. the PEEP level at which recruitment is maximized and over-distension minimized. Lung inflammatory markers obtained at 6 hours post recruitment via EIT will be compared with markers obtained 6 hours after the time when PEEP had been guided by the High-PEEP table. In addition, following crossover to the opposite group, biomarkers will be obtained after an additional 14 to 18 hours.

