# 2 Objectives

## 2.1 Primary Objective

- To compare the effect of EIT in patients with moderate to severe and severe ARDS for the optimization of PEEP titration with standard PEEP titration using the High-PEEP table on changes in relevant physiological and biomarker outcomes.

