### **5.1. Study Initiation**

At the time of randomization all study subjects will be receiving the standard University of Michigan ARDS protocol high PEEP arm (Appendix B). All patients will receive lung protective ventilation (LPV), attempting to achieve a plateau pressure (Pplat)  $\leq$  30 cm H2O with tidal volume by ideal body weight being allowed as high as 8 cc/kg and as low as 4 cc/kg in so doing.

Following randomization patients will undergo a mini-BAL according the methodology undertaken by Ranieri and colleagues [16] prior to institution of the protocol arm.

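### The 6-hour between-group comparison ignores the pre-treatment values the trial already collects; ANCOVA would be more precise if the two values correlate at about 0.5 or more

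*Combined protocol and SAP*

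**What the plan says.** Section 7 is the only statistical section. For the first period it says that "Usual care first and EIT first groups will be compared with each other at baseline and between groups at 6 hours". The tests follow by type of variable: "Quantitative, normally distributed variables such as cytokine levels and P/F ratio will be tested via t-test", and "Quantitative, non-normally distributed variables such as driving pressure and plateau will be tested via Mann Whitney test". No covariate or regression model is named, and no scale is given for the cytokines.

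The documents do not settle the analysis variable:

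- Section 1.1 reads as a comparison of levels: "Lung inflammatory markers obtained at 6 hours post recruitment via EIT will be compared with markers obtained 6 hours after the time" at which PEEP was guided by the table.
- Section 2.1 states the primary objective as an effect "on changes in relevant physiological and biomarker outcomes".
- Section 6.3 mentions only "between-group differences in several efficacy variables", which fits either reading.

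Pre-treatment values are planned. Under Section 5.1 the first mini-BAL is done "prior to institution of the protocol arm", and Appendix F marks cytokines at that sample. Section 6.2 records ventilator settings, pressures and a blood gas before the study starts. Where there are several values, "If more than one value is available for this 24-hour period, the value closest to the time of randomization will be recorded".

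**The concern.** Neither reading of Section 7 adjusts for baseline. A test of levels ignores the pre-treatment value. A test of changes subtracts all of it, which costs power against levels when r is below 0.5. Comparing the arms at baseline does nothing for the 6-hour comparison; after randomisation it can only describe chance imbalance.

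Section 1.1 singles out the 6-hour biomarker comparison. Only the first period has a 6-hour lavage under both methods, because the lavage after crossover comes at 14 to 18 hours. The comparison is between patients, so the crossover does not help its precision. At stake are its power and interval width, and a choice between levels and changes that could be made after the data are seen.

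The point covers the BAL biomarkers, PaO2, P/F, Pplat and the quantities calculated from ventilator settings. It does not cover the EIT measures, for which Appendix F has no baseline. Nor does it cover how to read the comparison made from the crossover point.

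**Working it through.** **Inputs from the documents.** Section 4.1 plans 20 patients. Section 4.6 has ten envelopes per sequence, so n = 10 per arm at most. No alpha, power, effect size, SD or correlation is stated, so there is no figure of the plan to reproduce.

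**Assumptions.** Two-sided alpha 0.05, effect of 1 SD of the 6-hour value, equal SDs at both times, normal data on the analysis scale, r from 0 to 0.7.

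**Formulas (SD = 1, 2/n = 0.2).**

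- Levels: SE = √0.2 = 0.447, 18 df, noncentral t.
- Changes: SE = √(0.2 × 2(1 − r)), 18 df. At r = 0.5 the factor 2(1 − r) equals 1, so power is the same as for levels.
- ANCOVA: SE = √(0.2 × (1 − r²)(1 + z²/S)), 17 df, with z² chi-square on 1 df and S chi-square on 18 df, averaged. This charges for the lost degree of freedom and for chance baseline imbalance.

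| | r = 0 | 0.3 | 0.5 | 0.7 |
|---|---|---|---|---|
| Power, levels | 56% | 56% | 56% | 56% |
| Power, changes | 32% | 43% | 56% | 78% |
| Power, ANCOVA | 54% | 57% | 66% | 82% |
| Effect at 80% power, levels (SD) | 1.32 | 1.32 | 1.32 | 1.32 |
| Effect at 80% power, changes (SD) | 1.87 | 1.57 | 1.32 | 1.03 |
| Effect at 80% power, ANCOVA (SD) | 1.37 | 1.31 | 1.19 | 0.98 |
| 95% CI width, ANCOVA / levels | 1.04 | 0.99 | 0.90 | 0.74 |

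The width ratio is √((1 − r²)(1 + 1/16)) × 2.110/2.101, since the mean of z²/S is 1/16. It does not depend on the effect size. ANCOVA breaks even with levels at r of about 0.25. Changes match ANCOVA only at r of about 0.9. In 40,000 simulated trials the powers agreed, and all three tests rejected a true null 4.8% to 5.1% of the time.

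**Smaller arms or effects.** At 8 per arm and r = 0.5, levels have 46% and ANCOVA 54%. At 10 per arm, r = 0.5 and an effect of 0.5 SD, the figures are 18.5% and 22.0%.

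**Variables assigned to Mann-Whitney.** On normal data with a 1 SD shift, the exact test has 51% power at its true size of 4.3%, or 54% if matched to 5%. Rank ANCOVA has 52%, 56%, 62% and 76% at the four r values. On skewed (log-normal) data with a 1 SD shift both tests do better. At r = 0.5 the gain is then about 9 points at log-SD 0.5 and about 4 at log-SD 1.0.

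**Scale of the biomarkers.** Assume log-normal values that EIT halves:

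| Log-SD | Raw t-test | Log t-test | Log ANCOVA, r = 0.5 | Log ANCOVA, r = 0.7 |
|---|---|---|---|---|
| 0.5 | 78% | 83% | 90% | 98% |
| 1.0 | 20% | 31% | 38% | 51% |
| 1.5 | 7% | 17% | 19% | 27% |

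Part of the raw test's shortfall is conservatism: its null rejection is 4.6%, 3.4% and 2.4%.

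**Missing first lavage.** Section 4.2 admits patients with P/F below 150, and Section 5.1.2 bars mini-BAL when P/F is below 100, so some patients can lack the baseline biomarker. With an assumed 4 of 20 baselines missing and a 1 SD effect:

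| r | Levels | Complete-case ANCOVA | ANCOVA, pooled baseline mean filled in |
|---|---|---|---|
| 0.3 | 55% | 45% | 56% |
| 0.5 | 55% | 52% | 62% |
| 0.7 | 57% | 71% | 75% |

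Null rejection with the pooled mean was 5.1% to 5.4%.

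**The case against.** The strongest objection is that r is unknown and may fall short of 0.5. The catheter is advanced blindly, the volume recovered varies, and no dilution correction is stated. A true correlation of 0.7 measured with reliability 0.7 at both times appears as 0.7 × 0.7 = 0.49. P/F is restricted in range by the entry limit and, among patients who have lavage, by the mini-BAL limit. Physiologic baselines may be up to 24 hours old. At r = 0.3 the gain over levels is one point. This stands, and it is why the claim is conditional on r.

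Several further points stand in part:

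- Levels is the more natural reading of Section 7, so the larger gains over change scores concern the less likely reading.
- A 1 SD effect flatters the difference in power. The interval width does not depend on it.
- Below r of about 0.25 adjustment loses slightly.
- The log scale is a separate improvement from covariate adjustment.
- The P/F bar also applies to the second lavage. Patients without a baseline sample may lack the outcome too, and filling in the baseline then rescues few of them.

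Finally, an unadjusted randomised comparison is valid, and this is a small single-centre study with no endpoint named as primary. That limits the severity. It is not a reason to leave a collected baseline sample unused.

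**Conclusion.** The concern holds. Section 7 gives the 6-hour comparison an unadjusted test on an unstated analysis variable, although a pre-treatment value is planned for the endpoints in question. Type I error is not inflated; the loss is efficiency in this one comparison.

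Against levels, ANCOVA at 10 per arm and a 1 SD effect costs about 3 points of power at r = 0, and gains about 10 at r = 0.5 (66% against 56%) and about 25 at r = 0.7 (82% against 56%). Against changes it is ahead at all four values of r, for example 57% against 43% at r = 0.3. The sizes rest on the assumed alpha, effect, r and normality. The gain may differ by endpoint, and is smaller for strongly skewed variables analysed by ranks. Even adjusted, 80% power needs an effect of about 1.19 SD at r = 0.5. This should be fixed, with medium confidence because r is unknown.

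**What to change.** Amend Section 7 before any analysis by arm:

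1. Analyse the 6-hour comparison by ANCOVA, with the 6-hour value as outcome and the same variable's pre-treatment value as covariate. Use the baseline of Section 6.2 or the first mini-BAL, not the Hour 0 reading, which is taken after PEEP is set. For variables now assigned to Mann-Whitney, use ANCOVA on ranks of both values and state how the effect will be estimated.
2. For a patient who lacks only the baseline value, fill in the mean of the observed baselines pooled over both arms. A missing 6-hour outcome (no second lavage or no blood gas) needs its own rule; this one does not repair it.
3. Analyse biomarkers on the log scale and report geometric mean ratios with 95% confidence intervals.
4. Describe the arms at baseline without significance tests.

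The cost is SAP wording and slightly more analysis, with no new patients, visits or samples. The statistical price is one degree of freedom and about 2 to 3 points of power against levels if r is near zero. The missing-baseline rule must be written in, because complete-case ANCOVA can do worse than the unadjusted test.
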